2 BACKGROUND AND RATIONALE

Stroke is a major cause of death and disability.^[1] Stroke patients have better care and outcomes if treated in a specialist unit.^[2-5] Not every hospital has a specialist stroke unit: patients are commonly triaged by prehospital clinicians, bypassing the nearest emergency department if a patient is thought to be suffering a stroke. Many patients present with stroke-like symptoms but have another condition which 'mimics' a stroke. This may be difficult to determine in the prehospital setting with the assessment deemed 'false positive',^[6] and the patient making an unnecessary journey to a specialist stroke team when in fact an alternative health care setting may be more appropriate (comprising up to 50% of all presentations to specialist stroke teams). This places avoidable pressure on ambulance and stroke services, with serious implications for quality of care for stroke and non-stroke patients.^[7] Remote prehospital triage may increase appropriate patient transfer, improving effectiveness and efficiency of ambulance, stroke, and other services, and the quality of care and outcomes for stroke and non-stroke patients.

During the first wave of the COVID19 pandemic, ambulance, and stroke teams in North Central (NC) London and East Kent developed and implemented prehospital video triage services, which used digital tools technology to permit remote communication between ambulance clinicians and stroke specialists. Through these services, stroke specialists can assess the patient while the patient is still on scene of the 999 call. The aim was to optimise individual patients' care: to ensure that stroke patients were taken to a stroke unit, and to minimise the number of non-stroke patients making unnecessary journeys to a stroke unit or hospital emergency departments (ED) if they could be managed by their GP or as an outpatient; these issues are important at any time, but became particularly urgent during the pandemic.

Reviewing existing evidence

Through a current service evaluation (discussed below),^[8] the team are conducting a two-phase literature review to assess the existing evidence base. The initial phase was a 'review of reviews' to identify existing systematic, scoping and narrative reviews on prehospital triage for

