Note. ^AControl for stroke patients is national, whereas the control for Ambulance data combines four NHS Ambulance trusts –meaning the stroke patient control is proportionally larger than the ambulance data control. ^BStroke case numbers drawn from the Stroke Sentinel National Audit Programme (SSNAP) data for April 2019 to March 2020. ^CNational data cover England, Wales, and Northern Ireland, excluding strokes reported for the case sites. ^DEast Kent data combine strokes reported for two sites: Queen Elizabeth the Queen Mother Hospital and William Harvey Hospital. ^EMaidstone data combine strokes reported for two sites: Maidstone General Hospital and Tunbridge Wells Hospital, the latter of which closed in late 2019, with stroke activity transferred to Maidstone. ^FAmbulance call sample based on estimates of 12 months of calls where ambulance crews have categorised patients as 'suspected stroke/neurological event', as provided by LAS, SECAmb, WMAS, and NEAS.

To study prehospital care, analyses will focus on job cycle time (from 999 call to 'ambulance free' time, where the ambulance is ready for its next dispatch); and initial patient destination. As these patient-level data are not held nationally the team will request these data from local ambulance services identified above. The team have confirmed with these organisations that the data are collected reliably and are available for request; and the costs agreed for these data requests have been included in the budget. Over the course of data requests researchers will work closely with Ambulance service representatives to ensure consistency of definitions and data collection. To study delivery of acute stroke care and stroke patient functional independence, researchers will analyse patient-level stroke national clinical audit data requested from SSNAP, and data collected by stroke teams using prehospital video triage. To study patient outcomes (patient mortality and length of hospital stay), researchers will analyse Hospital Episode Statistics data linked with Office for National Statistics mortality data, requested at patient-level from NHS Digital.

Source	Data	Measures	Time
Local ambulance	Patient-level	Call categorisation, Emergency Operations Centre	Apr 2019-

Table 4.Quantitative data sources

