	Patients categorised by ambulance crews as suspected stroke/neurologica	 Job cycle length, disaggregated by Time to dispatch; to scene; on scene; to hospital; Total job cycle Patient destination 	Aug 2022
Local stroke units	Patient-level	Stroke services using prehospital triage are collecting data on destination and diagnosis of all patients categorised as non-stroke	Apr 2019- Aug 2022
SSNAP	Patient-level Data for patients categorised as stroke	 Type of stroke (infarction/haemorrhage) Stroke severity (NIHSS¹) on arrival Patient characteristics (e.g. sex, age) Arrival mode (e.g. by ambulance, inhospital) Eligibility for thrombolysis Eligibility for mechanical thrombectomy Time from a) symptom onset, b) 999 call, and c) arrival at hospital to brain scan admission to stroke unit thrombolysis (if eligible) mechanical thrombectomy (if eligible) assessment by consultant physician assessment assessment by stroke specialist nurse swallow screen Outcomes: Functional independence: patients with Modified Rankin Scale score (established measure of stroke patient disability) of 0-2 (or return to baseline if baseline score is more than 2)	Apr 2019- Aug 2022
HES/ONS	Patient-level ED attendances (with dates); Stroke attendances	Emergency hospital admissions with dates and length of hospital stay All-cause patient mortality at 30 and 90 days	Apr 2019- Aug 2022

Note. ¹NIHSS=National Institutes of Health Stroke Scale.

Workstream 3: cost-effectiveness [RQ4; months 1-24]

In addition to understanding the effectiveness of pre-hospital triage it is also important to evaluate the cost-effectiveness of the intervention. Where possible the analyses will seek to understand if different triage systems deliver variable outcomes and costs, thereby informing any wider national scale-up.

The health economic analysis will focus on the case study sites and national and regional controls (Table 3). The analyses will draw on the same data sources as requested for Workstream 2 (Table 4), along with national reference costs and Trust estimates of service costs.

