Workstream 2. Patient conveyance, care delivery, and patient outcomes

The hypothesis is that prehospital video triage will a) reduce the number of inappropriate patient transfers to specialist stroke units, which will b) result in hyperacute treatments being delivered to stroke patients more quickly and reliably than elsewhere, and therefore c) that stroke patients treated by such services will have better outcomes than those treated by services that do not use prehospital video triage. To test these hypotheses, the analysis will use a controlled before-and-after design to estimate the impact of prehospital triage on ambulance journeys for suspected stroke patients:

Patient destination: the hypothesis is that there will be a significant reduction in the proportion of patients classified as 'suspected stroke/neurological' who are transferred to hospitals with specialist stroke units following implementation of prehospital triage services, relative to control sites.

The study will also analyse 'Job cycle' length (i.e., time from initial 999 call received through to 'ambulance free'), disaggregated by key processes (Table 4)

Furthermore, the analysis will estimate the impact on stroke patients receiving key clinical interventions, including:

- Time from onset of symptoms to receiving clinical interventions (to assess potential impact of increased time on scene to conduct prehospital triage)
- Time from arrival at hospital to receiving clinical interventions (to assess potential benefits of prehospital triage and advance knowledge of patients on effective running of stroke teams)
- Impact of these services on the following key outcomes
 - Patient mortality at 90 days (the primary outcome)
 - Patient functional outcome (as measured with the Modified Rankin Scale)

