These patient-level analyses will compare areas using prehospital triage (NC London, East Kent, Maidstone and Darent Valley) with other areas of England where prehospital triage is not used (hereafter referred to as the 'comparator') (Table 3), using propensity score matching (taking care to use only patient variables that should not be altered by the triage intervention, e.g. sex and age).^[32] A difference in differences (DiD) approach will be employed to understand the impact of the 'treatment effect' prehospital triage on outcomes (primary outcome: patient mortality at 90 days). DiD aims to generate causal effect estimates by comparing the change in the outcome from before to after the introduction of an intervention in the group exposed to the intervention, to the change in outcome from before to after the intervention in a group not exposed to the intervention. Provided a valid control group has been identified, the difference between the two differences can be said to represent the impact of the intervention.

As outlined above, the analysis will include a minimum of 12 months 'before' data and up to 26 months 'after' data. Given the sample sizes (Table 4), the team do not anticipate concerns about statistical power, but during the early stages of the study researchers will engage with clinical partners and data owners to understand the data in depth, and will conduct robustness tests alongside the main analyses.

Workstream timeline:

- Months 1-5: researchers work with clinical collaborators and data owners to gain a deeper understanding of the data available, specify data requests.
- Months 5-15: data requests submitted and data received to be prepared for analysis.
- Months 13-22: main analyses conducted, leaving time for integration of findings (see WS4).

Workstream 3: cost-effectiveness [RQ4; months 1-24]

In addition to understanding the effectiveness of pre-hospital triage it is also important to evaluate the cost-effectiveness of the intervention. Where possible the analyses will seek to understand if different triage systems deliver variable outcomes and costs, thereby informing any wider national scale-up.

The health economic analysis will focus on the case study sites and national and regional controls (Table 3). The analyses will draw on the same data sources as requested for Workstream 2 (Table 4), along with national reference costs and Trust estimates of service costs.

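### The destination and job-cycle cohort is defined by a crew code that on-scene video triage can influence, so its denominator can move with the intervention

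*Protocol*

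**What the plan says.** Protocol section 9, Workstream 2, states the destination hypothesis as a significant "reduction in the proportion of patients classified as 'suspected stroke/neurological' who are transferred to hospitals with specialist stroke units" after implementation, relative to control sites. Job-cycle length is analysed from the same ambulance data.

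Section 4 fixes who is in those data. Note F to Table 3 counts "calls where ambulance crews have categorised patients as 'suspected stroke/neurological event", and the ambulance row of Table 4 is restricted to "Patients categorised by ambulance crews as" suspected stroke/neurological. The same row lists "Call categorisation, Emergency Operations Centre" among its measures, but this does not define the cohort.

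Section 2 places the intervention at the same moment as the crew's contact: "stroke specialists can assess the patient while the patient is still on scene of the 999 call".

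Two safeguards are stated. Propensity-score matching is done "taking care to use only patient variables that should not be altered by the triage intervention" (section 9), and the team will work with the ambulance services to "ensure consistency of definitions and data collection" (section 4). Neither deals with entry to the cohort. No section says whether the crew code is recorded before or after the video call.

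**The concern.** A difference-in-differences on a proportion assumes that the rule for entering the denominator works the same way in all four cells (case and control areas, before and after). Here the rule is a judgement made by the people whose judgement the service is meant to inform. In one cell only, case areas after implementation, it can shift in two ways.

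- **Leaving.** A patient judged non-stroke on video may be given another code and never reach the extract. If that patient was also kept away from the stroke unit, a real success disappears from the denominator and the reduction is understated.
- **Entering.** With a specialist easy to reach, crews may apply the label to more borderline patients. If few of these go to a stroke-unit hospital, the proportion falls although no patient's destination has changed.

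Control crews have no triage, so subtracting their change removes neither effect. Matching on age and sex cannot bring back patients who were never requested.

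At stake is hypothesis (a), the most direct effect of the service, from which section 9 says (b) and (c) follow. Job-cycle length is exposed in the same way.

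**Working it through.** The protocol gives no baseline conveyance proportion, effect size or power figure for destination, so there is no figure to reproduce. The check is denominator arithmetic.

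**From the protocol (Table 3, annual calls):** case sites 1,729 + 2,529 + 2,620 + 984 = 7,862; control 46,724.

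**Assumed:** baseline proportion p0 (80%, range 60–90%); true proportion afterwards p1; share r of non-conveyed patients who lose the code; extra fraction m of patients coded; share s of those extra patients taken to a stroke-unit hospital.

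**Leaving.** Observed proportion = p1 / (1 − (1 − p1)·r). With p0 = 80% and p1 = 70% (true fall 10 points):

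- r = 10%: 0.70/0.97 = 72.2%, observed fall 7.8 points
- r = 20%: 0.70/0.94 = 74.5%, observed fall 5.5 points
- r = 30%: 0.70/0.91 = 76.9%, observed fall 3.1 points
- r = 41.7%: 0.70/0.875 = 80.0%, no observed fall

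At r = 20% the loss is 0.30 × 0.20 = 6% of coded calls, about 472 of 7,862 a year. Over p0 = 60–90%, a true 10-point fall is erased at r between 33% and 56%, and a true 5-point fall at r between 19% and 37%.

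**Entering.** Observed proportion = (p0 + m·s) / (1 + m), so the spurious fall is m·(p0 − s)/(1 + m). With p0 = 80%, no change in destinations and s = 0:

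- m = 2%: 0.80/1.02 = 78.4%, spurious fall 1.6 points
- m = 5%: 0.80/1.05 = 76.2%, spurious fall 3.8 points
- m = 10%: 0.80/1.10 = 72.7%, spurious fall 7.3 points

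At m = 5% that is about 393 extra calls a year over the four sites. Over p0 = 60–90% the fall at m = 5% is 2.9 to 4.3 points. It shrinks if some added patients are conveyed: with s = 40%, it is 0.05 × 0.40/1.05 = 1.9 points. It vanishes at s = p0.

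**Against the precision of the test.** With one year before and one year after, and calls treated as independent, SE = √[0.80 × 0.20 × (2/7,862 + 2/46,724)] = 0.69 points. A two-sided 5% test then needs a difference of about 1.96 × 0.69 = 1.35 points, so coding shifts of a few per cent are of the order that decides the result. This SE ignores clustering in four case sites. The true threshold is probably wider, so the comparison is indicative only.

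**What counts would show.** Per 1,000 baseline calls, leaving at r = 20% gives 700 transfers out of 940 coded calls. Entering at m = 5% with s = 0 gives 800 out of 1,050. In both cases the number of transfers is right and the movement in the denominator is visible, whereas the proportion alone shows neither.

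**The case against.** The strongest reply is that the decisive fact is missing. If the code is recorded before the video call, nobody can leave through it. Table 1 gives some support: three of the four sites triage all suspected strokes, so crew suspicion comes before triage. The label also covers neurological events, so many mimics could keep it. This stands, and it means the protocol shows a denominator that can move, not one that has moved. It does not close the second route, because access to triage may change whom crews suspect in the first place.

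Several further points stand:

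- Every drift input above is assumed, and the two routes have opposite signs.
- Table 4 says triage services collect destination and diagnosis for all patients categorised as non-stroke, which allows a case-site check on leavers.
- Table 4 does not establish that the call categorisation includes a stroke category or when it is set. A reader might infer that it should replace the crew code as the main denominator. The protocol does not support that, and such a cohort would miss strokes first suspected on scene.
- A reader might also see a contradiction between the number of transfers in hypothesis (a) and the proportion in the test. The second simply operationalises the first, and a proportion is defensible when areas differ this much in volume.

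The general safeguards answer less. Definitions can be identical everywhere while their application shifts after triage. Robustness tests cannot recover patients who were never in the extract.

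**Conclusion.** The concern holds as a risk built into the cohort definition. Entry to the destination and job-cycle analyses depends on a code that the intervention can influence in one of the four cells, and nothing in the protocol fixes that code before triage. Direction and size are unknown. Under the stated assumptions, plausible shifts move the destination result by roughly 2 to 7 points either way, which could hide or create a significant finding.

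Two stronger readings are not supported. One is that the destination result is already biased: the protocol says nothing about when the code is recorded. The other is that the main conclusion is at risk: the stated primary outcome is 90-day mortality from HES/ONS data, which this cohort does not define. The point should be fixed because it is cheap to address at data specification and hard to repair later, but it does not undermine the study.

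**What to change.** Keep the crew-coded cohort as planned and add three things.

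1. **Counts.** Report crew-coded calls and transfers to stroke-unit hospitals per area-month, and run a difference-in-differences on the crew-coded count beside the one on the proportion. A shift in the count is a warning rather than proof, because call volumes may also have changed differently between areas during the pandemic.
2. **Timing and a companion cohort.** In the data-specification phase (months 1–5), ask each ambulance service when the crew code is set relative to triage. If the call categorisation in Table 4 includes a stroke category set before crew contact, also request those calls whatever the crew later coded, and repeat the destination and job-cycle analyses on them.
3. **Leavers.** Use the case-site stroke-unit data on patients categorised as non-stroke to check how many triaged patients lost the crew code. These data exist only where triage is used, so they support a check and not a controlled comparison.

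State in advance that if the two cohorts disagree, the conclusion on hypothesis (a) will say so.

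The cost is a somewhat larger extract, possibly with an added data charge since request costs are already agreed in the budget, and a short analysis paragraph. The companion cohort would be less specific, which dilutes the effect, and would miss strokes first suspected on scene. For that reason it should stand beside the crew-coded cohort and not replace it.

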This research will take place in four areas of London and South East England where prehospital triage for stroke has been established. The focus of the research is on prehospital ambulance care and acute care settings, including stroke and emergency departments, but will also explore the organisations within which these services sit, and the wider context, including local/regional governance and commissioning, the voluntary sector, and other patient representative groups. In preparing the research application the team engaged with ambulance service leads in England and Wales, and clinical leads in Scotland (through the National Ambulance Stroke Leads group), who confirmed no other areas have implemented services of this kind at equivalent scale. Through this engagement with wider networks, the team were made aware of activity on prehospital triage for stroke in the East of England (plans to introduce a service, beginning with a pilot), and London (aims to roll out NC London model across the city). The team have engaged with people leading this activity in each area to ensure they are aware of this research, and they will to be added to the prospective stakeholder list (discussed further under Dissemination).

The study will analyse four case sites where prehospital triage has been implemented, summarised in Table 1. While similar in terms of platform and function, these case sites vary on a number of key features of the conceptual framework, including intervention characteristics (e.g., 24/7 coverage or patient eligibility), organisational characteristics (e.g. NHS Foundation trust status and academic links), and wider context (e.g., stroke system, rurality).

Characteristics	Case site				
	East Kent	NC London	Maidstone	Darent Valley	
Intervention characteristics					
Implemented from	Apr-2020	May-2020	Oct-2020	Nov-2020	
Platform	Facetime	Facetime	Facetime	Facetime	
Eligibility for assessment	All suspected strokes ¹	All suspected strokes	All suspected strokes	Diagnostic uncertainty	
Assessor	Consultant/ registrar	Consultant/ registrar	Stroke nurse, then consultant if needed	Stroke nurse, then consultant if needed	
Hours active	24/7	24/7	Stroke nurse: 24/7 Consultant: 8am- 8pm Mon-Fri	8am-6pm Mon- Fri	

Table 1. Characteristics of case sites

Organisation characteristics				
Acute FT-status	Yes	Yes	No	No
Acute Teaching	Yes	Yes	No	No
ED & Stroke unit co- located	No	No	Yes	Yes
Ambulance service	SECAmb	LAS	SECAmb	SECAmb
Wider context				

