Acute stroke system	Centralising	Centralised 2010	Centralising	Centralising
Rurality	Rural	Urban	Rural	Rural

Note. ¹East Kent eligibility was initially for patients where there was diagnostic uncertainty, and changed to all suspected strokes in September 2020.

Workstream 1: implementation and experiences [RQs 1&2; months 1-24]

The study will use a range of qualitative methods to analyse implementation and sustainability of prehospital triage services for stroke, and stakeholder experiences of these services, including patient, carer, and healthcare professional perspectives. The approach will draw on the chosen conceptual framework for implementation and sustainability of digital innovation,^[28] and it will be informed by the developing findings from the team's recent service evaluation of the NC London and East Kent services.

Stakeholder interviews

In each of the four case sites, up to 30 interviews will be conducted with a wide range of stakeholders to ensure suitable coverage of the services studied and the context in which they operate. Interviewees will include stroke and non-stroke (initially suspected to be stroke) patients and their carers, including patients with different decisions resulting from assessment (i.e., transferred to stroke unit, transferred to emergency department, referred to TIA clinic, advised to stay home). The team will work closely with clinical colleagues (including local research nurses) and purposively sample interviewees to ensure that a diverse range of patients and carers is recruited, in order to reflect local socio-demographic factors, including ethnicity, socio-economic status, language capabilities (e.g. non-English speakers) and living situation (e.g. patients who live alone). Interviews will also be conducted with clinical and managerial staff in ambulance services, acute stroke teams, and emergency departments, senior organisational management, and representatives of the wider context (Table 2).

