The analyses will focus on performance in the four case sites. For the comparative analyses of prehospital care the control cohort will include combined data from four ambulance NHS Trusts where prehospital triage services for stroke are not being used: London Ambulance Service NHS Trust (excluding NC London), South East Coast Ambulance NHS Foundation Trust (excluding East Kent, Maidstone, and Darent Valley), West Midlands Ambulance Service NHS Foundation Trust (WMAS), and North East Ambulance Service NHS Foundation Trust (NEAS). For the comparative analyses of delivery of stroke clinical interventions within hospital services the analyses will use a national control drawn from the Sentinel Stroke National Audit Programme (SSNAP). All patients submitted to these datasets will be included in prehospital and in/post hospital analyses.

Data

Table 3 presents annual activity levels in terms of prehospital care (patients who have been coded as *suspected stroke/neurological* by ambulance crews) and acute stroke care (number of

strokes reported in the national audit, the vast majority of whom are conveyed by ambulance). To enable the controlled before and after design, data covering a 40-month period (April 2019 to August 2022 inclusive) will be requested, permitting a minimum of 12 months 'before' data and minimum of 26 months 'after' data.

		Case sites			
Metric	Control ^A	East Kent	NC London	Maidstone	Darent Valley
Stroke patients treated in hospital ^B	85,549 ^c	970 ^D	1457	789 ^E	515
Ambulance calls for suspected stroke/neurological event ^F	46724	1729	2529	2620	984

Table 3.Annual activity for quantitative analysis

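### The patient-destination test counts arrivals at hospitals that have a stroke unit, so at Maidstone and Darent Valley it misses diversion to the same hospital's ED and understates any fall in stroke-unit transfers

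*Protocol*

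**What the plan says.** Protocol section 9, Workstream 2, opens with hypothesis (a): triage will "reduce the number of inappropriate patient transfers to specialist stroke units". The test that follows is a fall, relative to control sites, in the proportion of crew-coded suspected strokes "who are transferred to hospitals with specialist stroke units following implementation of prehospital triage services".

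Section 4, Table 1, has a row "ED & Stroke unit co- located". The entries are No for East Kent and NC London, and Yes for Maidstone and Darent Valley.

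Section 4 (Stakeholder interviews) lists the possible results of an assessment: "transferred to stroke unit, transferred to emergency department, referred to TIA clinic, advised to stay home". Sections 6.1 and 7 make the same distinction.

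On data, section 4 names job cycle time "and initial patient destination" as the prehospital measures, and Table 4 gives no department level for destination. Table 4 also describes a local dataset: "Stroke services using prehospital triage are collecting data on destination and diagnosis of all patients categorised as non-stroke".

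**The concern.** The hypothesis is about the stroke unit; the measure is about the hospital that contains it. The two agree only where the ED and stroke unit are in different hospitals. At a co-located site, a stroke mimic whom triage directs to the ED rather than the stroke unit still arrives at a hospital with a stroke unit, so the numerator does not change.

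Destination is the only stated test of the first link in the causal chain: fewer inappropriate transfers, hence faster treatment, hence better outcomes. Diverting mimics to a co-located ED could relieve the stroke team, which is the mechanism the protocol relies on, and the measure would not record it. Treatment times might then improve with less apparent change in destination than really occurred. Sites with different layouts would also not be measured on the same footing, although Workstream 3 wants to compare triage systems.

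**Working it through.** The protocol gives no effect size, baseline proportion or power figure for destination, so there is nothing to reproduce. It says only that "the team do not anticipate concerns about statistical power".

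**1. Share of calls at co-located sites.** Inputs are the Table 3 row "Ambulance calls for suspected stroke/neurological event": East Kent 1,729; NC London 2,529; Maidstone 2,620; Darent Valley 984; control 46,724.

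- All case sites: 1,729 + 2,529 + 2,620 + 984 = 7,862
- Co-located: 2,620 + 984 = 3,604; w = 3,604/7,862 = 0.458
- Not co-located: 1,729 + 2,529 = 4,258

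**2. The same share weighted by exposure.** Months from the Table 1 start date to August 2022 inclusive are 29, 28, 23 and 22. Calls × months:

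- East Kent 1,729 × 29 = 50,141
- NC London 2,529 × 28 = 70,812
- Maidstone 2,620 × 23 = 60,260
- Darent Valley 984 × 22 = 21,648
- Total 202,861; w = (60,260 + 21,648)/202,861 = 0.404

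**3. Attenuation.** Let D be the true fall in stroke-unit transfers and s the share of diversions that go to an ED. Assume the same D and s at every site, that ED diversions at the co-located sites go to the same hospital's ED, and that ED diversions elsewhere go to a hospital without a stroke unit. The co-located sites then show (1 − s)D, the other two show D, and the pooled case sites show (1 − s·w)D. The protocol does not give s, so a range is shown.

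| s (assumed) | Pooled, w = 0.458 | Pooled, w = 0.404 | Co-located sites alone |
|---|---|---|---|
| 25% | 0.885 D | 0.899 D | 0.75 D |
| 50% | 0.771 D | 0.798 D | 0.50 D |
| 75% | 0.656 D | 0.697 D | 0.25 D |
| 100% | 0.542 D | 0.596 D | 0 |

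For a true fall of 10 points, the pooled figure is 8.9, 7.7, 6.6 or 5.4 points with w = 0.458. The co-located sites alone show 7.5, 5.0, 2.5 or 0 points.

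**4. Equivalent sample-size factor, 1/(ratio²).** With w = 0.458 this is 1.3, 1.7, 2.3 or 3.4. At s = 100% with w = 0.404 it is 1/0.596² = 2.8.

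**5. Would the attenuated effect still be seen?** Assume independent calls, a proportion of 0.5, one year before, and Table 3 volumes after: 202,861/12 = 16,905 case-site calls, and 46,724 × 29/12 = 112,916 control calls. The difference-in-differences standard error is √[0.25 × (1/7,862 + 1/16,905 + 1/46,724 + 1/112,916)] = 0.0074, or 0.74 points. Even 5.4 points is 5.4/0.74 = 7.3 standard errors. Clustering by site would widen the standard error by an amount the protocol does not allow one to calculate.

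**The case against.** The strongest reply is that a hospital-level measure has its own logic. Section 9 introduces it as an effect on ambulance journeys, and redirection within one hospital changes no journey. That stands: the measure is valid for journeys, but incomplete for hypothesis (a).

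A reader might infer that the pooled effect is simply about halved, with a 3.4-fold loss of effective sample size. The documents do not support that. It requires every diversion to go to an ED, whereas the protocol also names home, TIA clinic, GP and outpatient care, all of which register at every site. It also requires equal diversion everywhere. Table 1 points the other way: Darent Valley assesses only uncertain cases, 8am to 6pm on weekdays (50 of 168 hours). And the protocol does not say where Maidstone's ED diversions go; a patient taken to a hospital without a stroke unit would count as a reduction.

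A reader might also infer that a working service would be reported as ineffective, or that site differences would reflect only layout. Neither is shown. Step 5 suggests underestimation rather than failure to detect, and the sites also differ in eligibility, assessor and hours. Nor does the protocol commit to one pooled destination estimate.

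Finally, section 4 promises work with ambulance services on consistent definitions, and section 9 sets aside months 1-5 for specifying data requests. That leaves room for a repair, but neither section mentions co-location.

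**Conclusion.** The mismatch is real and stands in the protocol's own text, so it is not a detail left to a later analysis plan. At Maidstone and Darent Valley the stated measure cannot register diversion to the same hospital's ED. It still registers the other diversions, so it is attenuated there rather than blind.

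A pooled effect would show between about 0.9 and 0.54 of its true size (0.90 to 0.60 with month weighting), depending on the ED share. This rests on an assumed ED share of 25% to 100%, equal diversion at each site and same-site ED diversion. Differences between sites would partly reflect co-location.

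The primary outcome (90-day mortality), functional outcome and treatment times are unaffected. This should be fixed, because it weakens the only stated test of hypothesis (a), but it does not undermine the main analysis.

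**What to change.** Define destination by receiving service (stroke unit, ED, other hospital, TIA clinic, not conveyed) in both case and control areas wherever ambulance records hold it, and ask for it when the data requests are specified in months 1-5.

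Where the receiving service is not recorded:

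- keep the hospital-level measure, labelled as an ambulance-journey outcome, and report it separately for co-located and non-co-located sites;
- base the test of hypothesis (a) on East Kent and NC London, against comparator areas with separate EDs where these can be identified (the protocol does not list them);
- for Maidstone and Darent Valley, report the proportion not conveyed or taken to a hospital without a stroke unit.

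Use the local stroke-unit data descriptively only. They cover triage services and patients classed as non-stroke, so they cannot supply the control side of the comparison.

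The cost is a change of outcome wording and possibly one more data field, whose availability the protocol does not establish. Under the fallback, precision is lower: the test of hypothesis (a) rests on 4,258 rather than 7,862 annual case-site calls.
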